9.2 Clinical Laboratory Tests

Summary statistics for mean and mean change from baseline in the routine clinical laboratory measurements, prolactin concentrations, coagulation parameters (PT, aPTT, and INR), HbA1c, and TSH will be provided by treatment and by visit.

Potentially clinically relevant laboratory measurement test results in the double-blind treatment period will be identified for the Safety Sample and will be summarized by treatment group and listed. Criteria for identifying laboratory values of potential clinical relevance are provided in Appendix 2.

9.2.1 Drug Induced Liver Injury (DILI)

Total bilirubin level should be checked for any subject with increased ALT or AST levels \geq three times the upper normal limits (ULN) or baseline.

- Reporting all DILI as SAE to the FDA based on Hy's Law:
 - \circ AST or ALT $> 3 \times ULN$ or baseline and
 - o T Bili $\geq 2 \times ULN$ or baseline

A separate incidence table will be provided for DILI cases, and the corresponding listing will be provided for Safety Sample during the double-blind treatment period.

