- 11) Subjects with uncontrolled hypertension, symptomatic hypotension, or orthostatic hypotension (see Section 8.7.3).
 - NOTE: Blood pressure measurements may be repeated once to ensure reproducibility of the exclusionary result(s) before excluding a subject based on the criteria noted above.
- 12) Subjects with epilepsy or a history of seizures, except for a single seizure episode; for instance childhood febrile, post traumatic, or alcohol withdrawal seizure.

Physical and Laboratory Results

13) Subjects with abnormal laboratory tests results, vital signs results, or ECG findings, unless, based on the investigator's judgment, the findings are not medically significant and would not impact the safety of the subject or the interpretation of the trial results. The medical monitor should be contacted to discuss individual cases, as needed

In addition, subjects with the following laboratory test and ECG results at screening must be excluded from the trial:

- Platelets $< 75000/\text{mm}^3$
- Hemoglobin $\leq 9 \text{ g/dL}$
- Neutrophils, absolute $\leq 1000/\text{mm}^3$
- $AST > 2 \times ULN$
- $ALT > 2 \times ULN$
- Creatine phosphokinase (CPK) > 3 × ULN, unless discussed with and approved by the medical monitor
- Creatinine $\geq 2 \text{ mg/dL}$
- QTcF \geq 450 msec in men and \geq 470 msec in women, unless due to ventricular pacing.

Tests with exclusionary results should be repeated to ensure reproducibility of the abnormality before excluding a subject based on the criteria noted above. For ECG, perform 3 consecutive recordings. If 2 of the 3 remain exclusionary then the subject must be excluded.

14) Subjects with a positive drug screen for cocaine or other illicit drugs are excluded and may not be retested or rescreened. Subjects with a positive urine drug screen resulting from use of cannabis, or prescription or over-the counter medications, or products that, in the investigator's documented opinion, do not signal a clinical condition that would impact the safety of the subject or interpretation of the trial results may continue evaluation for the trial following consultation and approval by the medical monitor. Subjects with positive results for alcohol use will require consultation and approval by the medical monitor in order to verify use does not indicate a substance-use disorder.

Disallowed and Concomitant Medication

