8.8.6 Potential Serious Hepatotoxicity

For a subject who experiences an elevation in AST or ALT that is ≥ 3 times the ULN, a total bilirubin level should also be evaluated. If the total bilirubin is ≥ 2 times the ULN, complete an IRE form with all values listed and also report as an AE on eSource.

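### The SAP's Hy's Law case rule adds a multiple-of-baseline alternative that the protocol does not have, so read literally it can tabulate subjects whose liver values are all normal

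*SAP*

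**What the plan says.** SAP 9.2.1 contains three statements that matter here.

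- **Trigger.** Bilirubin is to be checked when ALT or AST is at or above "three times the upper normal limits (ULN) or baseline".
- **Case definition.** It is introduced by "Reporting all DILI as SAE to the FDA based on Hy's Law". The transaminase limb reads "AST or ALT $> 3 \times ULN$ or baseline and", and the bilirubin limb reads "T Bili $\geq 2 \times ULN$ or baseline". Both limbs must be met.
- **Output.** "A separate incidence table will be provided for DILI cases", together with a listing, for the Safety Sample in the double-blind period.

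Protocol 8.8.6 starts from "an elevation in AST or ALT that is ≥ 3 times the ULN". It continues "If the total bilirubin is ≥ 2 times the ULN", in which case an immediately reportable event form and an AE entry are required. Neither threshold refers to baseline.

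Three other places bear on the point. SAP Appendix 2 and protocol Appendix 5 flag AST and ALT at 3 × ULN or more. Exclusion 13 in protocol 5.2.2 says that "subjects with the following laboratory test and ECG results at screening must be excluded from the trial"; the list includes AST and ALT above 2 × ULN but sets no bilirubin limit. SAP section 1 gives the SAP precedence where its analyses differ from the protocol's, so 9.2.1 would govern the table.

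**The concern.** The table built on SAP 9.2.1 does not count the event that the protocol defines. The baseline alternative is not limited to subjects who enter with raised values. For anyone whose baseline is below ULN it therefore lowers the bar, and for a low enough baseline the bar falls inside the normal range. The result is nevertheless presented under Hy's Law.

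Such tables are read case by case. A row made up of normal values, or a protocol-reported event absent from the table, would have to be explained after unblinding. The strict inequality is a second, smaller mismatch: it differs from the SAP's own trigger sentence, from SAP Appendix 2 and from the protocol.

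**Working it through.** The plan states no figure to reproduce here; the check compares two classification rules.

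**Notation.** A and A0 are on-treatment and baseline ALT (or AST). B and B0 are on-treatment and baseline total bilirubin.

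**Rules**

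- Protocol 8.8.6: A ≥ 3 × ULN and B ≥ 2 × ULN.
- SAP 9.2.1, literal: (A > 3 × ULN or A > 3 × A0) and (B ≥ 2 × ULN or B ≥ 2 × B0). This is the same as A > 3 × min(ULN, A0) and B ≥ 2 × min(ULN, B0).

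**Step 1: when can both values be normal?** We need 3 × A0 < A ≤ ULN, which is possible only if A0 < ULN/3. We also need 2 × B0 ≤ B ≤ ULN, which is possible only if B0 ≤ ULN/2. These conditions are in multiples of ULN and do not depend on any laboratory's limits.

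**Step 2: examples.** The documents give no ULN for ALT or bilirubin. Assume 40 U/L and 1.2 mg/dL, so that ULN/3 = 13.3 U/L and ULN/2 = 0.6 mg/dL.

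| ALT, baseline to on-treatment | Bilirubin, baseline to on-treatment | 3 × A0 | 2 × B0 | SAP case | Protocol case |
|---|---|---|---|---|---|
| 12 to 37 | 0.3 to 0.6 | 36 | 0.6 | yes | no |
| 10 to 31 | 0.3 to 0.6 | 30 | 0.6 | yes | no |
| 13 to 40 | 0.6 to 1.2 | 39 | 1.2 | yes | no |
| 14 to 40 | 0.6 to 1.2 | 42 | 1.2 | no | no |
| 10 to 31 | 0.7 to 1.2 | 30 | 1.4 | no | no |

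The first row (37/12 = 3.08; 0.6/0.3 = 2.0) stays entirely within normal limits for any ALT ULN of 37 U/L or more and any bilirubin ULN of 0.6 mg/dL or more.

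**Step 3: a value of exactly 3 × ULN.** Take A = 3 × ULN and B = 2.5 × ULN. The protocol counts it. The SAP's ULN limb alone does not, because 3 is not greater than 3. The baseline limb counts it when 3 × ULN > 3 × A0, that is, when A0 < ULN.

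| Baseline A0 (× ULN) | SAP, literal | Protocol |
|---|---|---|
| 0.3, 0.5, 0.9, 0.99 | counted | counted |
| 1.0, 1.2, 1.5, 2.0 | not counted | counted |

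**Step 4: after alignment.** With the protocol's thresholds, none of the Step 2 examples is a case, and the Step 3 value is a case at every baseline shown.

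**The case against.** **The baseline alternative may be meant for raised baselines.** This is the strongest reply. Exclusion 13 leaves room for it: ALT or AST between 1 and 2 × ULN is eligible at screening, and no bilirubin limit is listed. The purpose is plausible, but the SAP does not state the restriction. If baseline replaced ULN in those subjects, the transaminase threshold would run from 3 × 1 = 3 to 3 × 2 = 6 × ULN, which again differs from the protocol. Two programmers could derive different tables from the same data.

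**The case is rare and visible.** A false row needs a transaminase more than tripled together with bilirubin at least doubled. After baseline, chemistry is scheduled only at Week 6 and at Week 12 or early termination. The listing would let a reader look behind the row. All of this stands and keeps the point small.

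**The strict sign may be an artefact of the PDF text.** This cannot be excluded, and the sign should be confirmed in the source. The baseline problem does not depend on it.

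Three stronger inferences are tempting but not supported:

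- *That a value of exactly 3 × ULN is missed in general.* The literal reading that admits normal-range cases also counts this value whenever baseline is below ULN.
- *That a borderline case is lost to safety oversight.* At exactly 3 × ULN the SAP's bilirubin check still applies, SAP Appendix 2 still flags the value, and investigator reporting under protocol 8.8.6 is separate. Only the DILI table and listing could lose it.
- *That the 2.0 mg/dL bilirubin limit in SAP Appendix 2 shows a further conflict.* It is a single-analyte flag and not a ULN. The protocol's own Appendix 5 differs from its section 8.8.6 in the same way.

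**Conclusion.** Wrong as written, of minor severity. SAP 9.2.1 attaches an unrestricted baseline alternative to both limbs of a rule it labels Hy's Law, and protocol 8.8.6 has no such alternative. Read literally, the rule admits subjects with both values normal when baseline ALT or AST is below ULN/3 and baseline bilirubin is at or below ULN/2. The strict inequality, if confirmed, removes a value of exactly 3 × ULN only when baseline is at or above ULN.

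The effect is confined to the DILI incidence table and listing. Few subjects are expected to be affected, but the documents give no basis for estimating how many. For scale only, one false case among the planned 120 per arm is 1/120 = 0.8%.

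The conclusion rests on reading the baseline wording as a free alternative. The worked examples also rest on the assumed ULNs; the conditions in multiples of ULN do not.

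**What to change.** Reconcile SAP 9.2.1 with protocol 8.8.6 so that the table labelled Hy's Law rests on one stated rule, with the same ULN multiples and the same inequality as the protocol's event definition. Use that inequality in both the trigger sentence and the case definition. If multiples of baseline are still wanted, report them separately, say which subjects they apply to, and do not label them Hy's Law. Confirm the sign in the case definition against the source PDF at the same time.

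The cost is a few words in the SAP and one derivation flag. No new data are needed.

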9.2.2 Metabolic Change

In addition to mean change from baseline, incidence of treatment emergent significant changes in fasting lipids, fasting glucose, and metabolic syndrome will be summarized by treatment group using the following criteria.

Criteria for Treatment-Emergent Significant Change in Lipids and Glucose			
LAB PARAMETER	BASELINE ¹	ANYTIME POST BASELINE	
LDL Direct (FAS)ting	Borderline 100-<160	High >=160	
(MG/DL)	Normal/Borderline <160	High >=160	
	Normal <100	Borderline/High >=100	
	Any Value	Increased >=30	
HDL Cholesterol (FAS)ting	Normal >=40	Low <40	
(MG/DL)	Any Value	Decreased >=20	
Triglycerides (FAS)ting	Normal <150	High 200-<500	
(MG/DL)	Borderline 150-<200	High 200-<500	
	Normal/Borderline <200	High 200-<500	
	Normal <150	Borderline/High/Very High >=150	
	Any Value	Increased >=50	
Glucose Fasting, Serum	Normal <100	High >=126	
(MG/DL)	Impaired 100-<126	High >=126	
	Normal/Impaired <126	High >=126	
	Any Value	Increased >=10	

Criteria for Treatment-Emergent Metabolic Syndrome			
DESCRIPTION	ANYTIME POST BASELINE ¹		
Central Obesity	Waist Circumference >=102cm(MALE), >=88cm (FEMALE)		
Dyslipidemia	Triglycerides >= 150mg/dl		
Dyslipidemia	HDL < 40mg/dl (MALE), <50mg/dl (FEMALE)		
Supine Blood Pressure	Systolic>=130mmHg and Diastolic>=85mmHg		
Glucose Fasting, Serum	>=100mg/dl		
Metabolic Syndrome	Met 3 Or More of the Above Criteria at a Visit		

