5.2 Eligibility Criteria

5.2.1 Inclusion Criteria

Subjects are required to meet the following inclusion criteria at the time points described in the schedule of assessments (Table 1.3-1).

- 1) Male or female subjects, ages 18 to 65 years, inclusive, at the time of informed consent.
- 2) Subjects who are able to complete the consent process and/or consent obtained from a legally acceptable representative (as required by Institutional Review Board [IRB]/Independent Ethics Committee [IEC]) prior to the initiation of any protocol-required procedures.

- 3) Ability, in the opinion of the principal investigator, to understand the nature of the trial and follow protocol requirements, including the prescribed dosage regimens, tablet ingestion, and discontinuation of prohibited medication, and to read and understand the written word in order to be reliably rated on assessment scales.
- 4) Subjects with a primary DSM-5 diagnosis of BPD confirmed by the SCID-5-PD at screening.
- 5) At screening and Day 0, subjects must have a total score of \geq 12 on the ZAN-BPD scale. In addition, a score of \geq 2 in at least 2 of the following 4 ZAN-BPD subscale items will be required at screening and Day 0: 1) inappropriate anger, 2) paranoid ideation, 3) affective instability, and 4) impulsivity.
- 6) Subjects who, in the investigator's judgment, require treatment with a medication for BPD.
- 7) Subjects willing to discontinue all prohibited medications to meet protocol-required washouts prior to and during the trial period.

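### The SAP's treatment-emergent lipid table uses one HDL cut-off (40 mg/dL) for both sexes, while its other HDL rules use 50 mg/dL for women, so some newly low women go uncounted and some already low women are labelled normal

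*SAP*

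**What the plan says.** SAP 9.2.2 states that "incidence of treatment emergent significant changes in fasting lipids, fasting glucose, and metabolic syndrome will be summarized by treatment group", and gives the criteria in two tables.

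- **Lipid and glucose table.** HDL has two rows. The first is a shift between categories, "Normal >=40 Low <40", with no mention of sex. The second applies at any baseline value and counts a patient as "Decreased >=20" (mg/dL).
- **Metabolic-syndrome table.** The HDL criterion is "HDL < 40mg/dl (MALE), <50mg/dl (FEMALE".

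SAP Appendix 2 and Protocol Appendix 5 define HDL of potential clinical relevance as below 40 mg/dL in men and below 50 mg/dL in women. Both sexes are eligible ("Male or female subjects, ages 18 to 65 years, inclusive, at the time of informed consent", Protocol 5.2.1). The text gives no reason for the different female cut-off. Both tables in 9.2.2 carry a footnote mark whose text is not in the copy reviewed.

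**The concern.** The same measurement in the same woman is classed differently depending on the table. Between 40 and 50 mg/dL she is low in three of the four places that set an HDL threshold and normal in the fourth, which is the table meant to show new low HDL on treatment.

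The shift row therefore errs in both directions for women. It can leave out a woman who becomes low by Appendix 2, and it can count as new a woman whom Appendix 2 already called low at baseline. Incidence is tabulated by treatment group rather than by sex, so these women are mixed into the rate reported for each arm. What is at stake is the meaning of one reported safety incidence in a section devoted to metabolic change.

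**Working it through.** **1. The rules side by side (mg/dL)**

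| Place | Men, low | Women, low | Baseline condition as printed |
|---|---|---|---|
| SAP 9.2.2 lipid table, shift row | <40 | <40 | baseline >=40 |
| SAP 9.2.2 lipid table, fall row | fall >=20 | fall >=20 | any value |
| SAP 9.2.2 metabolic-syndrome table | <40 | <50 | none printed |
| SAP Appendix 2 | <40 | <50 | none |
| Protocol Appendix 5 | <40 | <50 | none |

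The rules agree for men. The conflict is confined to women between 40 and 50.

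**2. Individual cases, women (baseline to post-baseline)**

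| HDL | Shift row | Fall row | Newly low at 50 | Appendix 2 flag |
|---|---|---|---|---|
| 55 to 45 | no | no | yes | yes |
| 65 to 44 | no | yes (fall 21) | yes | yes |
| 52 to 38 | yes | no (fall 14) | yes | yes |
| 45 to 38 | yes | no (fall 7) | no, already low | yes |

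**3. Who is missed, without assumptions.** The shift row misses a woman who goes from >=50 to y, where 40 <= y < 50. The fall row recovers her only if baseline - y >= 20. Since y >= 40, her baseline must then be at least 40 + 20 = 60. Every woman who falls from 50 to <60 into 40 to <50 is therefore missed by both rows.

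**4. How many: illustration only.** The documents give no HDL distribution, between-visit correlation, expected drug effect or proportion of women, so there is no plan figure to reproduce. Assumed inputs for women:

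- mean m = 50 to 60 mg/dL
- SD = 12 to 15
- correlation between any two visits r = 0.60 to 0.85
- mean shift d = 0 to -3

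Protocol Table 1.3-1 schedules laboratory tests at Week 6 and Week 12/ET, and the lipid table counts any post-baseline value. The design-consistent model therefore has two post-baseline samples. Baseline X0 and post-baseline X1, X2 are jointly normal with means m, m + d, m + d. Let Y = min(X1, X2).

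- Newly low at 50: X0 >= 50 and Y < 50.
- Missed by the shift row: newly low and Y >= 40.
- Missed by both rows: also X0 - Y < 20.
- Counted by the shift row but already below 50: 40 <= X0 < 50 and Y < 40, as a share of all women with X0 >= 40 and Y < 40.

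Range over the grid of assumptions:

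| Quantity (women) | One post-baseline sample | Two samples |
|---|---|---|
| Newly low at 50, missed by shift row | 63-96% | 57-95% |
| Newly low at 50, missed by both rows | 51-95% | 44-94% |
| Counted by shift row, already <50 at baseline | 47-91% | 44-89% |
| Baseline 40 to <50, all women | 15-30% | same |

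For misses by both rows, the low end comes from mean 50, SD 15, correlation 0.60, shift -3. The high end comes from mean 60, SD 12, correlation 0.85, shift 0.

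**The case against.** **Tables need not share cut-offs.** Fasting glucose of potential relevance is 100 mg/dL or more in Appendix 2, yet the glucose shift rows count only 126 or more. A rise from 95 to 102 is caught by no glucose row, since it is a rise of 7 and the change row needs 10. A stricter shift threshold for HDL could be deliberate. This stands as a reason to ask for an explanation rather than assume a slip. It does not remove the labelling problem: glucose of 100 to <126 is called impaired, whereas HDL of 40 to <50 in women is called normal. The LDL and triglyceride rows of the same table also include the Appendix 2 cut-offs (160 and 150).

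**The women are still reported.** Any HDL below 50 in a woman is flagged under Appendix 2, summarised by arm and listed. It also counts towards metabolic syndrome, and mean HDL change is tabulated. This stands, and it limits the severity. As printed, however, those threshold rules carry no baseline condition and so do not separate new from pre-existing low HDL.

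**Stronger readings that a reader might infer.**

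- *The table misses most women who become low.* The documents cannot show this. With the fall row counted, the missed share drops below half at the low end of the assumed range (44%).
- *Most patients it reports as newly low already were.* The illustration contains no men, while the table pools the sexes. Among women alone the share can also be below half (44%).
- *The shift row is the only HDL summary that conditions on baseline.* The fall row is itself measured from baseline. The missing footnote text might also add a baseline condition to the metabolic-syndrome table.

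**Conclusion.** The inconsistency is real and needs no assumption to establish. For women, the lipid table's HDL shift row conflicts with the metabolic-syndrome table in the same section, SAP Appendix 2 and Protocol Appendix 5. Two consequences follow by logic: women who move from 50 or more into 40 to <50 are uncounted unless they fall by at least 20 mg/dL, and women who start at 40 to <50 are labelled normal and may be counted as newly low.

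The size cannot be derived from the documents. The 44% to 94% range for misses by both rows is conditional on the assumed normal distributions and two post-baseline samples. It shows that the effect could be substantial among women who cross 50, and it is not an estimate for this trial.

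This is a minor correction to one safety table. The rule is the same in both arms, and efficacy, type I error and sample size are untouched.

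**What to change.** Add a sex-specific HDL line to the lipid table in SAP 9.2.2, matching Appendix 2: men, baseline >=40 to post-baseline <40; women, baseline >=50 to post-baseline <50. Keep the existing <40 line for comparison with other trials in the programme, relabelled so that 40 to <50 is not called normal for women, and keep the row for falls of at least 20 mg/dL. If the single cut-off is intended, state the reason in 9.2.2 instead.

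The cost is one extra table row and its programming. HDL is already in the scheduled laboratory panel, so no new data are needed.

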8.7.3 Vital Signs

Vital signs will be collected at the time points described in the schedule of assessments (Table 1.3-1). Vital sign measurements scheduled for the same visit as blood samples are to be completed before blood is drawn. Subjects should be monitored for potentially clinically significant vital signs values (Section 10.6).

Vital sign measurements will include body weight, body temperature, systolic blood pressure (SBP), diastolic blood pressure (DBP), and heart rate. The following guidelines will aid in the standardization of body weight measurements:

- The same scale should be used to weigh a given subject each time, if possible.
- Scales should be calibrated and reliable; scales should be at zero just prior to each subject's weigh-in session.
- A subject should void prior to being weighed and be minimally clothed (ie, no shoes or heavy overgarments).
- Weight should be recorded before a subject's meal and at approximately the same time at each visit.

Blood pressure and heart rate measurements will be made in the supine and standing positions after the subject has been in position for at least 3 minutes. The supine measurements will be performed first, followed by standing.

Subjects with uncontrolled hypertension (screening DBP > 95 mmHg in any position) or symptomatic hypotension at screening or baseline are excluded from the trial as are subjects with orthostatic hypotension, which is defined as a decrease of ≥ 30 mmHg in SBP or a decrease of ≥ 20 mmHg in DBP within 3 minutes of standing compared with the previous supine blood pressure or development of symptoms. In addition, subjects should be excluded if they have any other vital sign measurement at screening or baseline that, in the investigator's judgment, is medically significant in that it would impact the safety of the subject or the interpretation of the trial results. However, any abnormal screening or baseline vital sign result(s) considered to be clinically significant should be repeated to confirm the finding(s) before excluding the subject from the trial.

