Appendix 1 Criteria for Identifying Vital Signs of Potential Clinical Relevance

Variable	Criterion Value ^a	Change Relative to Baseline ^a
Heart Rate ^b	> 120 bpm < 50 bpm	≥ 15 bpm increase ≥ 15 bpm decrease
Systolic Blood Pressure ^b	> 180 mmHg < 90 mmHg	≥ 20 mmHg increase ≥ 20 mmHg decrease
Diastolic Blood Pressure ^b	> 105 mmHg < 50 mmHg	≥ 15 mmHg increase ≥ 15 mmHg decrease
Orthostatic Hypotension	≥ 20 mmHg decrease in systolic blood pressure and a ≥ 25 bpm increase in heart rate from supine to sitting/standing	Not Applicable (baseline status not considered)
Weight	-	≥ 7% increase ≥ 7% decrease

^a In order to be identified as potentially clinically relevant, an on-treatment value must meet the "Criterion Value" and also represent a change from the subject's baseline value of at least the magnitude shown in the "Change Relative to Baseline" column.

^b As defined in "Supplementary Suggestions for Preparing an Integrated Summary of Safety Information in an Original NDA Submission and for Organizing Information in Periodic Safety Updates," FDA Division of Neuropharmacological Drug Products draft (2/27/87).

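### The blood pressure component of metabolic syndrome counts only when systolic and diastolic are both raised, so isolated elevation of either is not scored, and the SAP does not say why

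*SAP*

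**What the plan says.** SAP 9.2.2 (Metabolic Change) plans an incidence of treatment-emergent metabolic syndrome by treatment group. Its table has five components:

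- Central obesity: "Waist Circumference >=102cm(MALE), >=88cm (FEMALE" (limits by sex).
- Triglycerides: "Triglycerides >= 150mg/dl".
- HDL: "HDL < 40mg/dl (MALE), <50mg/dl (FEMALE" (limits by sex).
- Supine blood pressure: "Systolic>=130mmHg and Diastolic>=85mmHg".
- Glucose: "Glucose Fasting, Serum >=100mg/dl".

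The syndrome is then defined as "Met 3 Or More of the Above Criteria at a Visit".

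Two other places set blood pressure limits. SAP Appendix 1 has separate systolic and diastolic rows for values of potential clinical relevance; the diastolic limits are "> 105 mmHg < 50 mmHg" and the high systolic limit is 180 mmHg. A footnote there also requires a stated change from baseline. Protocol 8.7.3 excludes at entry "Subjects with uncontrolled hypertension (screening DBP > 95 mmHg in any position"), a rule on diastolic pressure alone.

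Protocol 8.7.2 and the schedule of assessments place waist measurement at screening and at Week 12 or early termination. Laboratory tests after baseline are at Week 6 and Week 12 or early termination.

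**The concern.** Read literally, the blood pressure row is the only one of the five that needs two abnormal measurements at once. A programmer would code it that way, and subjects with raised systolic pressure alone or raised diastolic pressure alone would be recorded as not meeting the component. Neither document gives a reason for this.

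The other blood pressure threshold table does not fill the gap. Appendix 1 starts above 180 mmHg systolic or 105 mmHg diastolic and adds a change from baseline. Isolated moderate elevation therefore enters no planned blood pressure incidence count; it appears only in the summary statistics of SAP 9.3.

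Safety and tolerability are the secondary objective in SAP section 2, and Protocol 2.3 gives increased weight as the most frequent adverse event under brexpiprazole (12.1%). A metabolic summary in this trial should be reasonably sensitive, and it should be clear that any insensitivity was chosen.

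**Working it through.** The documents state no incidence of metabolic syndrome, so there is no figure of theirs to reproduce. The direction can be shown by logic; the size needs assumed inputs.

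**1. Direction at one visit.** Take the four other components as met or not (16 patterns), and systolic and diastolic each as high or not (4 patterns): 16 x 4 = 64 combinations. Score each under *and* and under *or*.

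- Twelve combinations change, all from no syndrome to syndrome.
- In each of them exactly two other components are met (6 patterns) and exactly one pressure is high (2 patterns): 6 x 2 = 12.

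So at a single visit the joint rule cannot give a higher count.

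**2. Where it can act.** The rule needs three components at the same visit. All five are available after baseline only at Week 12 or early termination. At Week 6 waist is absent, which leaves four. At the other scheduled visits neither waist nor laboratory values are planned.

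**3. Size at one visit (assumed inputs).** None of these values comes from the documents.

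- Supine pressures bivariate normal: systolic mean 118-125, SD 12-14; diastolic mean 75-78, SD 8-9 mmHg; correlation 0.5-0.7.
- Other components independent: waist 40%, triglycerides 30%, HDL 35%, glucose 25%.

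For the other four components:

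- P(all 4) = 0.40 x 0.30 x 0.35 x 0.25 = 0.0105
- P(exactly 3) = 0.0315 + 0.0195 + 0.0245 + 0.01575 = 0.09125
- P(exactly 2) = 0.0585 + 0.0735 + 0.0455 + 0.04725 + 0.02925 + 0.03675 = 0.29075

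Hence P(syndrome) = 0.10175 + 0.29075 x P(blood pressure component). The two extremes of relative loss are:

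| Assumed systolic; diastolic (mean, SD); correlation | Both high | Either high | Syndrome, *and* | Syndrome, *or* | Relative shortfall |
|---|---|---|---|---|---|
| 118, 12; 75, 8; 0.7 | 0.064 | 0.200 | 0.120 | 0.160 | 25% |
| 125, 14; 75, 8; 0.5 | 0.075 | 0.391 | 0.124 | 0.215 | 43% |

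Over the whole grid:

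- both pressures are high in 5-17% and either is high in 20-44%;
- the joint rule keeps 19-42% of subjects with either pressure raised;
- prevalence is 11.5-15.1% under *and*, against 16.0-23.0% under *or*.

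A second assumed set covers lower pressures (means 115/73 to 123/79, SD 12-15 and 8-10, correlation 0.6-0.7) with each other component at 20-40%. The prevalence gap runs from 0.049 - 0.032 = 1.7 percentage points to 0.320 - 0.244 = 7.6 points, or about 2 to 9 subjects per 120 with complete data.

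**4. Treatment-emergent cases.** If emergent means absent at baseline, the ordering in step 1 need not hold for every subject. Take someone with two other components throughout, 135/80 at baseline and 135/88 on treatment. That is a new case under *and*, but already positive at baseline under *or*.

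A simulation assumed means 122/77, SD 13/9, systolic-diastolic correlation 0.6, the component rates of step 3, between-visit correlation 0.6-0.8 and other correlations 0-0.3:

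- between 1% and 2% of subjects are emergent only under *and*;
- the net shortfall in emergent counts is about 15-25%, against 24-33% for prevalence on the same inputs;
- it exceeds 15-25% if the denominator is subjects without the syndrome at baseline.

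**The case against.** The strongest reply is that the documents cite no reference definition of metabolic syndrome. Without one, *and* is not demonstrably an error, and a shortfall exists only relative to an either/or rule. This stands. A reader might infer that true cases are being missed; the documents support only the statement that the joint rule is stricter and unexplained.

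Several supporting arguments are also weaker than they look:

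- A reader might take the Appendix 1 rows as showing that either pressure suffices alone. They do not, because the footnote also requires a change from baseline. The same table contains a deliberate joint criterion: orthostatic hypotension needs a systolic fall and a heart-rate rise.
- The diastolic limit in Protocol 8.7.3 is an entry criterion and says little about scoring a syndrome component.
- Triglycerides and HDL are two components. By that pattern blood pressure would give two rows, not one *or* row.
- A reader might infer that the lower count costs precision. That is unsupported: at these rates a rarer event has a smaller binomial variance, SAP 9.2.2 specifies no test, and no between-arm effect was modelled.
- The prevalence figures ignore baseline, although the table concerns treatment-emergent cases. Baseline handling may be in the table's footnote, which is not readable in the available text; that is not held against the plan.

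Blood pressure, weight, waist, lipids and glucose are each summarised separately, so the underlying data are not lost.

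What the reply does not supply is a reason for the joint rule, or another planned incidence table that would show isolated moderate elevation.

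**Conclusion.** The point holds as a minor improvement to a descriptive safety table. What is certain is that the row requires both pressures, that the other four components each need one measurement, that no explanation is given, and that at any one visit the joint count is the same as or below an either/or count.

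The size is not certain. On the first assumed set in the working, single-visit prevalence falls by roughly a quarter to two-fifths; the treatment-emergent shortfall of about 15-25% comes from one simulation. Independence between components drives part of this: within the simulation, positive correlation reduced the relative loss. These figures are illustrations, not estimates for this trial.

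The same rule applies to both arms. The primary and key secondary analyses do not use it.

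**What to change.** Before unblinding, change the row in SAP 9.2.2 to: Systolic >=130 mmHg or Diastolic >=85 mmHg (supine). Apply the same definition at baseline and after baseline, and state how a subject who already meets the syndrome at baseline is handled. If the joint rule is wanted for comparison with earlier tables, show it as a second, labelled line.

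The cost is one word in a SAP table and one programming condition, plus one table line if both rules are shown. Reported incidence will probably be somewhat higher in both arms, and the main line may be less comparable with any earlier tables that used the joint rule. Settling it before unblinding keeps the choice independent of the results.
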